## Assessment Battery

The assessment battery will consist of the following: (1) Community Reintegration of Injured Service members – Computer-Adaptive Test (CRIS-CAT), a commonly used measure of community reintegration following deployment; (2) Short-Form 12 Health Survey (SF-12), measures eight domains related to physical and mental health, health perceptions, and the impact of physical or emotional problems on general functioning via self-report; (3) Beck Anxiety Inventory (BAI) assesses the severity of anxiety symptoms, minimizing those that overlap with depression; (4) Beck Depression Inventory - Second Edition (BDI-II) assesses severity of depressive symptoms; (5) Quality of Life Enjoyment and Satisfaction Questionnaire- Short Form (Q-LES-Q-SF) is a brief, 16-item measure of subjective functioning and satisfaction across a range of life domains including work, leisure activities, social relationships, and physical health; (6) Saint Louis University Mental Status Exam (SLUMS) is an 11-item clinician-administered screening measure of cognitive impairment; (7) Anxiety Disorders Interview Schedule DSM-5 (ADIS-5) is a gold-standard semi-structured clinician interview used to assess for the presence of all anxiety disorders including PTSD. Modules examining the presence of psychosis, mood and

substance abuse disorders are also included; (8) Demographic and Military Survey is a brief questionnaire we have used in previous studies that inquires about general demographic and military information. Veterans are asked about their periods of service, deployment dates, whether they seek healthcare outside of VA, and other information pertaining to their education and employment history; (9) Perceived Barriers to Seeking Mental Health Services (PB-SMHS) assesses concerns specific to Veterans that are related to seeking mental health counseling and related services; and (10) Client Satisfaction Questionnaire-8 (CSQ-8) is a brief 8-item measure used to assess overall treatment satisfaction. All measures will be administered at each assessment period, except the ADIS-5, Q-LES-Q-SF, SLUMS, Demographic Questionnaire, and PB-SMHS, which will only be administered at baseline. The CSQ will only be administered at 1-month and 3-month follow-up periods. The complete battery of assessments can be administered in 2-3 hours.

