Statistical Methods

Specific Aim 1: Examine the effectiveness of iCBT in improving community reintegration and overall quality of life. Community reintegration will be measured using the 3 subscales of the CRIS-CAT: extent of participation, perceived limitations, and satisfaction with participation. Quality of life will be measured by the SF-12 Physical Component Summary (PCS) and Mental Component Summary (MCS) scores. Although our quantitative analyses will be intention-to-treat, we will provide information on the number of and characteristics of any participants who did not receive the treatment as allocated or who did not complete the study. We will tabulate baseline characteristics, such as age, race, gender, disease severity, comorbidities, and psychotropic medications. Based on recommendations of the CONSORT group,⁸¹ we will adjust analyses for variables we have decided *a priori* may be important to control (i.e., depression, period of service [OEF/OIF/OND, Gulf War, and other] concomitant psychotropic medication use, and the primary diagnosis stratification variable). Results from both an intent-to-treat and treatment completer analyses will be compared.

Hypothesis 1a: *iCBT and sCBT will significantly improve community reintegration and quality of life relative to TAU at 3-and 6-month follow-ups.* To compare changes between the iCBT, sCBT, and TAU groups at all time periods in a single regression, we will use a hierarchical mixed-model analysis. Because the number of patients randomized to the 3 groups is not equal, we will test for unequal variances and if necessary, will account for this in our regression models. For outcomes with unequal variances, in the mixed model, we will estimate the variances separately and adjust the degrees of freedom for the unequal variances. The model will contain terms for the intercept, treatment, time period and interaction between time and treatment. *A priori* covariates as well as the stratification variable of anxiety disorders will also be included in the model. A significant time-by-treatment interaction will be followed by pairwise contrasts to determine whether the active interventions differed from TAU and whether the active treatments differed from each other. We will report the p-values and adjust p-values post-hoc using multiple comparisons procedures (e.g., Bonferroni) as recommended in the literature.⁸²

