Hypothesis 1b: *iCBT will result in improved reintegration/quality of life measures relative to sCBT at 1-month follow-up.* Only patients in the iCBT and sCBT groups will be used in the analyses. For each outcome, we will run a hierarchical linear regression model using the baseline and 1 month data and with the *a priori* covariates and anxiety disorder stratification variables. Patients will be nested within therapist. The models will contain the 1 month value as the outcome variable and the baseline value of the outcome as an additional covariate. A significant value for the parameter estimate for the intervention will indicate that the iCBT and sCBT groups differed at 1 month.

Specific Aim 2: Examine the effectiveness of iCBT in reducing anxiety/depression symptoms relative to sCBT and TAU. **Hypothesis 2a:** *iCBT and sCBT will significantly reduce anxiety and depression symptoms relative to TAU at 3-and 6- month follow-ups.* The analyses described for hypothesis 1a will be repeated for this hypothesis using the secondary outcomes. Anxiety will be measured using the BAI and depression measured using the BDI-II. **Hypothesis 2b:** *iCBT will result in improved anxiety/depression measures relative to sCBT at 1-month follow-up.* The analyses described for hypothesis 1b will be repeated for this hypothesis using the secondary outcomes.

Specific Aim 3 (Exploratory): Hypothesis 3a: *Compare rates of psychotherapy engagement in iCBT relative to sCBT.* We will use hierarchical logistic regression models to test if the iCBT and sCBT groups differed on treatment engagement (defined as the percentage of randomized patients who participated in 12 or more treatment hours). The outcome will be whether or not

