the patient completed 12 or more treatment hours. The a priori variables to be included as independent variables in the treatment engagement model will be selected based on the SOTA Access model described earlier. Items comprising the subscales of geographical, temporal, financial, and cultural barriers will be selected from the PB-SMHS measure for inclusion. The model will also include intervention group and our primary diagnosis stratification variable. To account for clustering, we will nest patients within therapist. **Hypothesis 3b:** Examine heterogeneity of treatment effects on 3- and 6-month outcomes. Because our sample size may not be adequate to substantiate sources of heterogeneity of treatment effects (HTE), exploratory analyses will allow us to describe patterns that can be examined in future larger trials. We will assess HTE on 3-and 6- month effectiveness outcomes through examining potential moderators collected at baseline including demographics, geographic region, co-occurring depression, psychiatric comorbidity, and medication use. Examining the role of potential moderator variables will provide a better understanding of how individuals vary in their response to iCBT and the conditions under which iCBT may be optimal. Following the approach suggested by Kent et al⁸³ for assessing HTE, we will use a multivariable prediction tool to report how relative and absolute risk reduction varies by baseline risk. We will use an internally-developed model from a regression analysis of data from the active treatment arms. Per Brookes et al⁸⁴, we will test the interaction terms in the models as the most statistically robust approach to assessing HTE.

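### Exploratory Hypothesis 3b promises relative and absolute risk reductions for outcomes that are scores with no defined event, and names no contrast for a risk model fitted in the active arms only

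*SAP*

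**What the plan says.** SAP, Specific Aim 3, Hypothesis 3b examines whether treatment effects at 3 and 6 months differ between patients. It has three strands.

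- **Measure.** A multivariable prediction tool, following a cited approach, will "report how relative and absolute risk reduction varies by baseline risk".
- **Source of the risk model.** "We will use an internally-developed model from a regression analysis of data from the active treatment arms".
- **Test.** "we will test the interaction terms in the models as the most statistically robust approach to assessing HTE".

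The stated interest is "how individuals vary in their response to iCBT and the conditions under which iCBT may be optimal". The status is modest: "exploratory analyses will allow us to describe patterns that can be examined in future larger trials".

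The outcomes come from earlier SAP sections. Specific Aim 1 uses three CRIS-CAT subscales and the SF-12 PCS and MCS. Specific Aim 2 uses the BAI and BDI-II. All are analysed as scores in mixed or linear models. Hypothesis 1a plans contrasts for "whether the active interventions differed from TAU and whether the active treatments differed from each other", and Hypothesis 2a extends this: "The analyses described for hypothesis 1a will be repeated for this hypothesis using the secondary outcomes".

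Protocol F2, Assessment Battery, repeats the measures at every assessment "except the ADIS-5, Q-LES-Q-SF, SLUMS, Demographic Questionnaire, and PB-SMHS, which will only be administered at baseline". The CSQ-8 is given at 1 and 3 months only.

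**The concern.** A risk reduction compares the probability of an event between arms. Hypothesis 3b names this measure for outcomes that have no event. Anyone carrying out the analysis would have to choose a cut-off for each scale, possibly after seeing the data. That choice matters because a treatment that shifts every patient's mean score by the same amount still gives an absolute risk reduction that varies with baseline risk, in a direction set by the cut-off. The purpose of 3b is to pass patterns on to later trials, and such a pattern could be passed on as a finding.

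There is also a second gap. The risk score is built from iCBT and sCBT patients only, and 3b does not say which arms are then compared. A score fitted in one of the compared groups and not the other follows chance variation in the first. Its slope then looks steeper there even if the treatment effect is the same for everyone.

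**Working it through.** Hypothesis 3b states no figure of its own to reproduce.

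**Step 1. Is there an event anywhere?**

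| Candidate | Why it does not serve |
|---|---|
| CRIS-CAT, SF-12 PCS/MCS, BAI, BDI-II | Scores; no responder or remission rule in the documents provided |
| ADIS-5 diagnosis | Baseline only (Protocol F2), so no diagnostic remission at follow-up |
| Q-LES-Q-SF of 42 or lower | An eligibility rule; the scale is baseline only |
| CSQ-8 | A satisfaction score with no cut-off |
| 12 or more treatment hours | Binary, but the engagement outcome of Hypothesis 3a, not a 3- or 6-month effectiveness outcome |

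**Step 2. What a later cut-off would do.** The 0.50 SD effect is the planning value in Protocol G1. Assumed inputs are a score R-squared of 0.3 and comparator event rates of 20%, 50% and 80%. The outcome has SD 1, higher is worse (a scale running the other way is reversed first), and active treatment lowers everyone's mean by 0.5. For standardised score z and cut-off c = Φ⁻¹(1 − event rate), which is 0.842, 0 or −0.842:

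- comparator risk = 1 − Φ[(c − √0.3·z)/√0.7]
- active risk = 1 − Φ[(c + 0.5 − √0.3·z)/√0.7]

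Each is averaged over a tertile of z. ARR is the difference and RRR is 1 minus the ratio, both taken before rounding.

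| Comparator event rate | Tertile | Comparator risk | Active risk | ARR | RRR |
|---|---|---|---|---|---|
| 20% | bottom | 5.1% | 1.3% | 3.7% | 73.6% |
| | middle | 16.0% | 5.7% | 10.4% | 64.6% |
| | top | 38.9% | 19.9% | 18.9% | 48.7% |
| 50% | bottom | 25.1% | 10.7% | 14.4% | 57.4% |
| | middle | 50.0% | 27.8% | 22.2% | 44.5% |
| | top | 74.9% | 54.1% | 20.8% | 27.8% |
| 80% | bottom | 61.1% | 38.8% | 22.3% | 36.4% |
| | middle | 84.0% | 65.7% | 18.3% | 21.8% |
| | top | 94.9% | 85.6% | 9.3% | 9.8% |

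Check: at 20%, the overall active risk is Φ(Φ⁻¹(0.20) − 0.5) = 9.0%, so ARR is 11.0%. The tertile mean is (3.7 + 10.4 + 18.9)/3 = 11.0%.

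Over R-squared 0.05 to 0.5, the top-minus-bottom ARR difference is +5.8 to +20.7 points at 20%, +2.3 to +9.2 at 50%, and −4.8 to −18.4 at 80%. With an effect of 0.1 SD instead of 0.5 (R-squared 0.3), all nine ARRs lie between 1.1% and 4.7%.

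**Step 3. Score fitted in the active arms, then tested against TAU.** This was simulated with 4,000 trials per setting, a 0.5 SD main effect, no true interaction, independent predictors of equal weight and no therapist clustering. The number of predictors and R-squared (0.05 to 0.5) are assumed. Arm sizes are 95/95/62 (Protocol G1), or 76/76/50 after 20% loss (0.8 × 95 = 76; 0.8 × 62 = 49.6). G1 gives that loss for 1 month only, so its use at 3 and 6 months is an assumption. The nominal error rate is 5%.

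| Predictors | 76/76/50 | 95/95/62 |
|---|---|---|
| 5 | 5.5–9.1% | 4.9–8.5% |
| 8 | 6.6–16.5% | 6.6–15.7% |
| 12 | 8.6–28.1% | 8.6–25.0% |

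The high ends occur at R-squared 0.05. The same score used for iCBT vs sCBT gives 4.2–5.8%. A score fitted in all arms pooled gives 4.4–5.6% (active vs TAU) and 4.2–5.9% (iCBT vs sCBT).

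In tertiles against TAU, the spurious top-minus-bottom difference averages 0.04 to 0.46 SD, against a sampling SD of 0.29 to 0.39. It is below its sampling SD in 28 of 30 settings. The two exceptions have 12 predictors at R-squared 0.05.

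**The case against.** - **The analysis is exploratory and mostly runs as written.** This stands. Moderator-by-treatment interactions can be tested on the scores. A reader might infer that 3b as a whole cannot be done, but only the risk-reduction reporting is undefined. The exploratory label excuses low power, not an undefined measure.
- **The event may be defined elsewhere.** The SAP text appears to be an extract: Hypothesis 3a refers to a model described earlier that is in neither document, and the citations start at 81. The point is therefore limited to the documents provided.
- **The 0.5 SD illustration presumes a contrast with TAU.** This stands. Hypotheses 1a and 2a expect benefit over TAU at 3 and 6 months; superiority of iCBT over sCBT is hypothesised only at 1 month (1b, 2b). A reader might infer that the reversal appears under any contrast. The missing event does apply to all of them, but the size of the distortion does not.
- **The two risk measures simply conflict.** A reader might infer this from the 20% rows, where ARR rises while RRR falls. At 50% and R-squared 0.3, however, ARR peaks in the middle tertile, so there is no general opposition.
- **Overfitting will produce false heterogeneity.** The documents do not support this. It requires the score itself to be stratified on or tested against TAU. The interaction terms may mean only the listed moderators, and the iCBT wording also fits a comparison with sCBT, where there is no bias.
- **Varying ARR is a true property of a binary endpoint.** Correct. It follows that fixing a cut-off in advance prevents later choice but does not remove variation that comes from the scale.

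**Conclusion.** The concern holds as a minor point. In the documents provided, the relative and absolute risk reductions of Hypothesis 3b cannot be computed, because no event is defined for any 3- or 6-month effectiveness outcome. This needs no modelling assumption.

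The consequence depends on the contrast. Against TAU with a constant 0.5 SD effect and an assumed R-squared of 0.3, the cut-off alone can make absolute risk reduction rise, fall or peak in the middle across score tertiles. With an effect near zero, as may apply to iCBT vs sCBT at 3 to 6 months, the differences are small.

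The overfitting point is secondary. If the active-arms score is used against TAU, the false-positive rate is about 5–9% with 5 predictors and up to about 28% with 12 weak ones, under assumed predictor counts and R-squared. The bias is usually smaller than chance variation. Comparisons of iCBT with sCBT and single-moderator tests are unaffected. A reader should not carry any of this over to Aims 1 and 2, whose analyses do not use the score or a risk scale.

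**What to change.** Amend Hypothesis 3b as follows.

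1. Replace risk reductions with mean differences and confidence intervals on each outcome's own scale, across score strata.
2. Fit the score in all three arms pooled, with a treatment main effect and no treatment-by-predictor terms. In the simulation this held the error rate for either contrast.
3. Name the contrast or contrasts, and say whether the score is itself tested or only used to describe.
4. If risk reductions are kept, pre-specify one responder definition per outcome and state that variation in absolute risk reduction across strata can arise from the scale alone.

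The cost is SAP wording only, with no new data, visits or patients.
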